NON-INTERVENTIONAL (NI) STUDY PROTOCOL

Study Information

Title	REGISTRY OF COMPLETE RESPONSES TO SUNITINIB IN SPANISH PATIENTS WITH METASTATIC RENAL CELL CARCINOMA (ATILA STUDY)
Protocol Code	A6181227
Protocol Version	Version 1.0 of 18 th October 2018
Date of the latest Protocol version	18 th October 2018
Active substance	Sunitinib Malate
Drug	SUTENT®
Objectives of the registry:	
To identify patients with metastatic renal cell carcinoma (mRCC) who obtained complete response (CR) to treatment with sunitinib alone or with sunitinib and a local treatment to eliminate residual disease and achieve CR in the clinician's opinion.
 
The clinical baseline characteristics of these patients and the tumour will be described in order to find predictive factors of response.
 
The aim is to describe the therapeutic strategy adopted in patients who obtained greater clinical benefit in the cases described once the macroscopic lesions have been eradicated in order to draft recommendations to follow once the statistical analysis of the registry is available.

PFIZER CONFIDENTIAL

Authors:

PPD MD PhD

Medical Oncologist

PPD

PPD MD

Senior Medical Advisor GU Pfizer

PPD

Pfizer Oncology Medical Department

Tel.: PPD

Email: PPD

This document contains confidential information belonging to Pfizer. Unless otherwise agreed in writing, on accepting or reviewing this document, you agree to keep this information confidential and not to copy it or disclose it to others (except when required by applicable law) or to use it for unauthorised purposes. In the event of any actual or suspected non-compliance with this obligation, Pfizer should be promptly notified.

TABLE OF CONTENTS

TABLE OF CONTENTS.....	3
1. LIST OF ABBREVIATIONS.....	5
2. PERSONS RESPONSIBLE FOR THE STUDY	9
3. ABSTRACT.....	10
4. AMENDMENTS AND UPDATES.....	16
5. MILESTONES.....	16
6. STUDY RATIONALE	17
7. HYPOTHESIS AND OBJECTIVES	26
7.1. Primary objectives:.....	26
7.2. Secondary objectives:.....	27
7.3. Exploratory analysis:.....	28
8. METHODS OF INVESTIGATION.....	28
8.1. Study design.....	28
8.2. Scope	29
8.2.1. Inclusion Criteria	30
8.2.2. Exclusion Criteria	30
8.3. Variables.....	31
8.4. Source documents.....	33
8.5. Sample size.....	33
8.6. Treatment of data.....	34
8.6.1. Case Report Forms (CRFs)/Data Collection Tools (DCTs)/Electronic Data Record.....	34
8.6.2. Records preservation.....	34
8.7. Data analysis	35
8.8. Quality control.....	35
8.9. Research methods limitations.....	36

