2 INTRODUCTION

The purpose of this Statistical Analysis Plan (SAP) is to provide a detailed description of the statistical analyses that will be performed to generate the final report for the ATILA study. This includes a brief summary of the main study characteristics and the aim of the SAP, which refers to the statistical analysis plan for this study.

CR to a tyrosine kinase enzyme inhibitor (TKI) is rarely achieved in clinical trials for the treatment of metastatic renal carcinoma, where the classic description of CR only provides for pharmacological treatment, and this response is evaluated either by the study investigator or by a centralized radiological committee (most common situation).

Since the eradication of all measurable lesions will be achieved in a small percentage of patients, the Sunitinib summary of product characteristics does not provide guidelines on the therapeutic strategy to be followed in these cases, i.e. continue the treatment and at what dose or discontinue it indefinitely.

The purpose of this registry is to shed some light on this issue, reviewing what was done in these patients in order to write useful recommendations for the clinician facing this dilemma.

➤ Data from phase III clinical trials

In the Sunitinib pivotal clinical trial (Motzer et al., 2007), the interim analysis, and according to RECIST criteria, no patient achieved CR to treatment according to the central radiological committee, whereas according to the researchers there was one patient with CR, which meant less than 1% of the subjects who participated in the clinical trial. However, in the final analysis published 2 years later (Motzer et al., 2009), 11 patients (3%) in the Sunitinib arm reached CR to treatment according to the investigator.

In the Sorafenib clinical trial, TARGET study (Escudier et al., 2007), there was no patient with CR according to the independent committee in the interim analysis, while one case of CR was described by investigator (<1%).

In the phase III trial of Pazopanib versus placebo (Sternberg et al., 2010), there was one patient in the interim analysis who achieved CR to treatment with Pazopanib (<1%) according to the independent radiological committee.

In the COMPARZ study (Motzer et al., 2013), according to an independent radiological committee, 3 patients achieved CR to treatment with Sunitinib versus 1 patient in the Pazopanib treatment arm.

➤ **Data from expanded access programmes:**

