Of the total cohort, 65 patients discontinued therapy in the absence of a documented relapse. The reasons were: medical or patient decision in 57 cases and 8 due to toxicity. Another 18 patients dropped out of the treatment due to disease progression at the time of the cut-off, while 17 patients were still on first-line treatment even although all their lesions had disappeared.

A second PFS was also defined as the time elapsed since the CR was obtained until the relapse of the disease or death from any cause; PFS from CR: it reached 2.3 years (27.6 months).

Of the 30 patients who discontinued treatment after reaching CR, 14 had progressed at the time of data cut-off, 12 of whom received a second-line treatment, including 4 subjects who were re-treated with the same drug. The median PFS of this second line was 14.5 months.

The authors' conclusions were that patients who achieved CR to an TKI had an excellent long-term prognosis, with very long PFS and OS.

No association was found between overall survival and progression-free survival after CR and the baseline prognosis group according to MSKCC.

There were no significant differences in survival between patients who decided to continue treatment after the disappearance of the lesions and those who discontinued it.

In the European Urology editorial, [name] and [name] (Alimohamed and Sridhar, 2016), emphasised the importance of maintaining a balance between efficacy and toxicity in cases in which the decision is taken to continue treatment with TKIs after

the total eradication of the lesions. The patient's point of view is important. Discontinuing treatment may generate anxiety in some people.

On the other hand, continuing treatment once the CR is reached may promote resistance to it.

Observing the disappearance of lesions from the radiological point of view does not exclude the presence of viable tumour cells.

➤ **Baseline characteristics associated with CR:**

Factors such as age do not seem to influence the impact of TKI on the tumour.

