5 OBJECTIVES AND VARIABLES

The primary objective of the study is *to identify patients with metastatic renal cell carcinoma (mRCC) who obtained a complete response (CR) to treatment with Sunitinib exclusively or with Sunitinib and a local treatment to eliminate residual disease in the opinion of the clinician. Complete response (CR) is defined as the disappearance of all measurable lesions according to the investigator's criterion in at least 2 consecutive CT scans.*

The clinical baseline characteristics of these patients and the tumour will be described in order to look for predictive response factors.

[figure not shown]
The intention is to describe the therapeutic strategy used in patients who obtained the greatest clinical benefit in the cases described once the macroscopic lesions were eradicated in order to draft recommendations to be followed once the registry's statistical analysis is available.

The variables to be analysed for this study will be obtained from the patients' medical records and case report forms according to the protocol. The data will be recorded on the paper CRF designed for this study where the following patient information will be included:

DEMOGRAPHIC AND DISEASE INFORMATION

- 1) Age at the start of treatment for metastatic disease
- 2) Functional status, measured by the ECOG scale (0, 1, 2, 3, 4) and/or by means of the KPS (Karnofsky Performance Status) scale, at the start of treatment (see annex I)
- 3) Motzer and Heng prognostic criteria
- 4) Laboratory data (haemoglobin, leukocytes, corrected calcium, LDH levels, lymphocytes, platelets, neutrophils, lymphocytes)
- 5) Comorbidities
- 6) Date the disease was diagnosed
- 7) Metastasis site(s) and number
- 8) Furhrman grade (I, II, III, IV)

PFIZER CONFIDENTIAL

- 9) Tumour stage (TNM)
- 10) Previous nephrectomy
- 11) Necrosis

TREATMENT

- 1) Start date of treatment with first-line Sunitinib
- 2) Initial dose and treatment regimen
- 3) Type of treatment received (monotherapy or in combination with local treatment) and technique used in the case of local treatment
- 4) Response to treatment.
- 5) Date of completion of the treatment after CR if treatment is interrupted
- 6) Modification of dosage and/or treatment regimen, number of changes in the dose, reason, date and new dose
- 7) Dose interruptions, number of interruptions, reason, date of interruption and restart and new dose

CCI

- 9) Adverse reactions

POST-TREATMENT

- 1) Continuation of treatment in 1st line

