5.1 EFFICACY/EFFECTIVENESS OBJECTIVES

Efficacy is assessed by describing the complete responses in daily clinical practice in Spain in patients with metastatic renal carcinoma treated with first-line Sunitinib, defined as the documented disappearance of all lesions in the investigator's opinion in at least 2 consecutive CT scans. The treatment may be with Sunitinib alone (CR Suni) or Sunitinib plus a local treatment to eliminate residual disease (CR + local treatment).

The baseline characteristics of both patient and tumour will be described to seek predictive response factors. The following variables will be considered:

- Demographic characteristics (age at the start of treatment)
- Comorbidities: cardiac, renal, endocrine, autoimmune and hepatic.
- Previous nephrectomy
- Classification of the risk group according to Motzer and/or Heng criteria and of the association between each one of the prognostic variables, such as: patient baseline status, time elapsed from nephrectomy to the start of systemic treatment, presence of anaemia, corrected calcium, LDH levels, neutrophil and platelet levels.
- Tumour data: histology, Fuhrman grade, presence of tumour necrosis and number and location of metastases (organs involved).

Secondary efficacy objectives evaluated will be time on treatment with Sunitinib until CR, duration of complete response and the time elapsed from CR to disease stabilisation/progression or change of treatment due to unacceptable toxicity or death from any cause.

The subjects with the greatest clinical benefit will be evaluated on the basis of the therapeutic strategy adopted in order to develop recommendations to be followed in patients who obtain CR. Moreover, the decision to discontinue treatment after a period of maintenance of CR and the pharmacological group by the mechanism of action used in second line after disease the progression will be evaluated.

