is monotherapy or combination with a local treatment for one or several residual lesions. In the group of patients who received local treatment, the frequency distribution of the techniques used (traditional surgery, radiotherapy and SBRT) will be presented, at the time they are applied, as well as histology, degree of tumour necrosis and the surgical complications reported.

In the sub-sample of patients who discontinue systemic treatment after a period of treatment with maintenance of CR, the most frequent reasons for the decision and the frequency of cases in which the patient was consulted in the decision to discontinue treatment will be reported, and the cases in which it was at the patient's or the investigator's request.

The distribution of frequencies of the pharmacological group by mechanism of action used in patients in the second-line treatment after disease progression will be reported.

Once the descriptive statistics have been presented, and provided that the proportional *hazards* assumption or relative risk of the covariates of interest (patient and tumour baseline conditions, dose and treatment regimen and type of treatment received) are fulfilled, a multivariate Cox regression will be performed to investigate the effect of all prognostic factors on CR/PFS. The *hazards ratio* (HR) will be estimated, along with their 95% confidence intervals, as parameters of association between each one of the predictive factors of response and the time to complete remission or disease progression.

This information will make it possible to produce recommendations for the therapeutic strategy to be followed in patients who obtain complete remission of the macroscopic lesions to the treatment with Sunitinib.

For the safety analysis of treatment with Sunitinib, the percentage of patients who have presented serious and non-serious adverse events explicitly attributed to Sunitinib during treatment will be presented by means of descriptive tables. The frequency of adverse events recorded will be reported based on severity, the highest grade and whether it or they led to a dose interruption or modification.

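### The SAP promises recommendations on strategy after complete response, but no planned analysis relates stopping or continuing sunitinib to outcome, and its stated route to them most naturally reads as selecting patients on outcome

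*SAP*

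**What the plan says.** - **The question.** SAP 2 says the product label gives no guidance after CR on whether to "continue the treatment and at what dose or discontinue it indefinitely". It also reports that an earlier Czech registry found no significant survival difference between "patients who decided to continue treatment after the disappearance of the lesions and those who discontinued it".
- **The promise.** SAP 7.2.4, after the Cox model: "This information will make it possible to produce recommendations for the therapeutic strategy to be followed in patients who obtain complete remission".
- **The route.** SAP 5: "The intention is to describe the therapeutic strategy used in patients who obtained the greatest clinical benefit". SAP 5.1: "The subjects with the greatest clinical benefit will be evaluated on the basis of the therapeutic strategy adopted in order to develop recommendations". The registry objectives at the front of the protocol similarly aim to "describe the therapeutic strategy adopted in patients who obtained greater clinical benefit". Neither document defines the benefit or gives a cut-off. The secondary objective in Protocol 7.2 and SAP 2.2 is worded differently: it ranks strategies by benefit rather than picking patients, but gives no method.
- **What is said about stopping.** SAP 5.1 says the decision to discontinue during maintained CR will be evaluated. SAP 5.4 labels definitive interruption after CR, and treatment time after CR, as covariates.
- **The model.** The Cox regression is "to investigate the effect of all prognostic factors on CR/PFS", with "covariates of interest (patient and tumour baseline conditions, dose and treatment regimen and type of treatment received" as its named inputs. Stopping or continuing is not among them.

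**The concern.** The registry exists largely to inform the stop-or-continue decision, so readers will look for evidence on it. The plan leaves them a statement that recommendations will follow, and a description of what was done in the patients who did best. Stopping happens after CR, and only a patient still in remission can stop electively. The longer the remission, the more time there is to stop. A description confined to the best outcomes can therefore show a high proportion of stoppers purely because of elapsed time, and a reader could take that as support for stopping. The opposite group, patients who progressed early, had little chance to stop and will look like continuers.

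**Working it through.** **Step 1. Look for a stop-or-continue analysis in SAP 7.2.**

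| Place | What is planned | Links stopping to outcome? |
|---|---|---|
| 7.2.2 | Summary statistics for treatment time after CR | No |
| 7.2.3 | Frequency of interruption and definitive discontinuation, with reasons | No |
| 7.2.4, log-rank | Baseline variables against time to CR | No |
| 7.2.4, patients who stop in CR | Reasons and patient involvement | No |
| 7.2.4, Cox | Baseline conditions, dose and regimen, type of treatment | No |

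Type of treatment means sunitinib alone or with local treatment. Dose and regimen appear in 7.2.2 as the initial ones. SAP 4.4 gives subgroups as not applicable. Protocol 8.7 allows a stratified analysis, but it is optional, depends on the results and names no factor.

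**Step 2. Size of the timing artefact.** The plan has no figure to reproduce, so this is an illustration with a true effect of nil.

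Input from the documents: median PFS from CR of 27.6 months in the cited Czech registry (SAP 2).

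Assumed: exponential times, follow-up uniform on 4 to 132 months, a fraction p stopping at CR and the rest with median stop time m months, and a split by quartile of observed time from CR.

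- The probability of still being under observation and progression-free at x months (x of 4 or more) is 2^(−x/27.6) × (132 − x)/128. At x = 9.7 this is 0.784 × 0.955 = 0.75. At x = 41.4 it is 0.354 × 0.708 = 0.25. These are the quartile boundaries.
- The share stopped among patients with observed time x is 1 − (1 − p) × 2^(−x/m).
- With p = 0 and m = 12, the share is 1 − 2^(−9.7/12) = 43% at the lower boundary and 1 − 2^(−41.4/12) = 91% at the upper. Every patient in the shortest quartile lies below the first figure and every patient in the longest above the second. Simulated averages (300,000 patients) are **24% and 96%**.
- With p = 0.5 and m = 48, the boundary values are 1 − 0.5 × 2^(−9.7/48) = 57% and 1 − 0.5 × 2^(−41.4/48) = 72%. Simulated averages are **54% and 80%**.
- With p = 1 everyone has stopped and the contrast vanishes.

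These two scenarios were chosen because each gives about 65% stopping overall, matching the 65 of 100 in the Czech registry who discontinued without documented relapse (57 by medical or patient decision, and 8 of 65, or 12%, for toxicity). That is an anchor only. The same account also mentions 30 patients who discontinued after reaching CR. A scenario with about 30% stopping (p = 0, m = 48) gives 60% in the longest quartile against 7% in the shortest.

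**Step 3. Does a different analysis remove it?** Splitting each patient's time into on and off treatment, the rate ratio is (events off ÷ time off) ÷ (events on ÷ time on). Under the same null it is 0.99 to 1.02, so the timing artefact disappears. By contrast, a fixed ever-stopped covariate gives Cox hazard ratios of 0.13 to 0.39 with no stops at CR (m from 6 to 48), and 0.17 to 0.61 with half stopping at CR, when the truth is 1.0.

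**Step 4. Precision at 90 patients.** Expected events = 90 × [1 − (27.6 ÷ (128 × ln 2)) × (2^(−4/27.6) − 2^(−132/27.6))] = 90 × [1 − 0.311 × (0.904 − 0.036)] = 90 × 0.73 = about 66. With p = 0 and m = 12, the simulated standard error of the time-dependent log hazard ratio is about 0.32. The 95% interval around a hazard ratio of 1 is then exp(±1.96 × 0.32), about 0.53 to 1.88.

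**The case against.** The strongest reply is that the registry is declared purely descriptive, with no hypothesis, so leaving out a stop-or-continue comparison is legitimate. This largely stands: the plan need not contain that comparison, and with about 90 patients it could well be inconclusive. It does not rescue a promise of recommendations, or a description conditioned on outcome.

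It can also be said that part of strategy is analysed. That is correct: dose and regimen, and local treatment, enter the Cox model. The gap concerns stopping or continuing.

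Third, the greatest-benefit wording states an intention. SAP 7.2 contains no such table, and SAP 5.1 could be read as assessing benefit by strategy. This stands in part. Selection on outcome is the natural reading of SAP 5 and of the protocol's front-page objectives, but not the only possible one. The quartile split above is an illustrative device that does not appear in the SAP.

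A reader might go further and infer that the SAP will enter ever-stopped as a fixed covariate, because SAP 5.4 calls it a covariate and 7.2.4 speaks of all prognostic factors. The documents do not support that. The inputs named in 7.2.4 omit it, and 5.4 gives the same label to cause of death and the reason CR ends, so it may be only a data list. Equally, it would be wrong to infer that the SAP ignores stopping, since 5.1 says the decision will be evaluated. What is missing is a method and an outcome.

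**Conclusion.** The point holds in this form: the SAP sets stop-or-continue as its question and claims its results will support recommendations, but it specifies no analysis relating that choice to outcome. The route it describes can make stopping look like a feature of good outcome when it reflects time in remission. With no true effect and about 65% stopping, the illustrated contrast is 96% against 24%, or 80% against 54% when half stop at CR. The direction follows from the time ordering whenever some stops occur after CR. The size rests on the assumed stop times, share stopping at CR, follow-up and quartile split, none of which the documents give for this registry.

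The documents do not support a claim that the registry's results as a whole are biased. The primary description of CR does not depend on this. A time-dependent analysis would remove the timing artefact but not confounding by the reasons for stopping.

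**What to change.** 1. In SAP 5 and 5.1, with matching wording in the protocol's objectives, replace the greatest-benefit selection with a description of all evaluable patients by post-CR strategy: off at CR, stopped later (with date and reason), or continued. Do not show PFS or duration-of-response curves by ever-stopped group, since they carry the same artefact.
2. State in SAP 7.2.4 that the post-CR variables listed in 5.4 will not be entered as fixed covariates.
3. If stopping is related to outcome, start at CR confirmation and use on/off status as a time-dependent covariate, or a prespecified landmark. Take progression or death as the outcome, report toxicity-driven treatment change separately, and label the analysis exploratory.
4. Amend the recommendation sentence in 7.2.4 so that anything drawn from the registry is called hypothesis-generating.

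The cost is SAP wording, a matching edit to the protocol objectives, and a little programming for item 3. The SAP already lists the treatment-end, progression and death dates, so no new data are needed. Protocol 8.7 lets the SAP modify the planned methods, and the definition and analysis of the primary objective do not change. The downside is the wide interval in item 3 (about 0.53 to 1.88 around a hazard ratio of 1), so items 1, 2 and 4 are the minimum. No clinical rule is proposed.

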ANNEX I: ECOG VS KARNOFSKY EQUIVALENCE TABLE

ECOG	KARNOFSKY
0	100-90%
1	80-70%
2	60-50%
3	40-30%
4	20-10%

PFIZER CONFIDENTIAL
